## Appendix A.2: Response Determination for Chronic GvHD

Response Determination for Chronic GVHD Clinical Trials based on Clinician Assessments

Organ	Complete Response	Partial Response	Progression
Skin	NIH Skin Score 0 after previous involvement	Decrease in NIH Skin Score by 1 or more points	Increase in NIH Skin Score by 1 or more points, except 0 to 1
Eyes	NIH Eye Score 0 after previous involvement	Decrease in NIH Eye Score by 1 or more points	Increase in NIH Eye Score by 1 or more points, except 0 to 1
Mouth	NIH Modified OMRS 0 after previous involvement	Decrease in NIH Modified OMRS of 2 or more points	Increase in NIH Modified OMRS of 2 or more points
Esophagus	NIH Esophagus Score 0 after previous involvement	Decrease in NIH Esophagus Score by 1 or more points	Increase in NIH Esophagus Score by 1 or more points, except 0 to 1
Upper GI	NIH Upper GI Score 0 after previous involvement	Decrease in NIH Upper GI Score by 1 or more points	Increase in NIH Upper GI Score by 1 or more points, except 0 to 1
Lower GI	NIH Lower GI Score 0 after previous involvement	Decrease in NIH Lower GI Score by 1 or more points	Increase in NIH Lower GI Score by 1 or more points, except from 0 to 1
Liver	Normal ALT, alkaline phosphatase, and Total bilirubin after previous elevation of 1 or more	Decrease by 50%	Increase by 2 × ULN
Lungs	
 
- Normal %FEV1 after previous involvement
 
- If PFTs not available, NIH Lung Symptom Score 0 after previous involvement
 
	
 
- Increase by 10% predicted absolute value of %FEV1
 
- If PFTs not available, decrease in NIH Lung Symptom Score by 1 or more points
 
	
 
- Decrease by 10% predicted absolute value of %FEV1
 
- If PFTs not available, increase in NIH Lung Symptom Score by 1 or more points, except 0 to 1
 

Joints and fascia	Both NIH Joint and Fascia Score 0 and P-ROM score 25 after previous involvement by at least 1 measure	Decrease in NIH Joint and Fascia Score by 1 or more points or increase in P-ROM score by 1 point for any site	Increase in NIH Joint and Fascia Score by 1 or more points or decrease in P-ROM score by 1 point for any site
Global	Clinician overall severity score 0	Clinician overall severity score decreases by 2 or more points on a 0-10 scale	Clinician overall severity score increases by 2 or more points on a 0-10 scale

ULN indicates upper limit of normal.

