3.2. Study Endpoint(s)

Endpoints will be further defined in subsequent sections. Unless otherwise specified, time-to-event endpoints will be calculated from the date of HSC infusion. If a patient received more than one HSCT, the time of the last HSC infusion immediately preceding infusion with BPX-501 will be the transplant date.

Primary Endpoint:

Event-Free Survival (EFS) at 180 days. Events are defined as the first occurrence of either transplant-related mortality (TRM) for non-malignant patients or non-relapse mortality (NRM) for malignant patients, severe GvHD (Grade 2-4 acute organ GvHD or extensive/moderate-severe chronic GVHD), and life-threatening infections (Grade 4).

NB: In the BPX-501 protocols, the terminology 'extensive' chronic GvHD was used. For the purposes of the primary analysis and for the rest of this SAP, extensive chronic GvHD will be defined as moderate or severe chronic GvHD. 'Overall' chronic GvHD or chronic GvHD without a qualifier will be interpreted as mild, moderate or severe chronic GvHD.

The following secondary endpoints are in the BP-004 protocols, although additional endpoints and analyses are described below in subsequent sections of this document.

Secondary Endpoints:

- (i) Transplant-Related Mortality (TRM) in patients with non-malignant diagnoses or Non-Relapse Mortality (NRM) in patients with malignant diagnoses at 100 and 180 days
- (ii) Cumulative incidence and severity of acute GvHD (any Grade 2-4 or Grade 3-4) as well as overall and moderate-severe chronic GvHD at 180 days.
- (iii) Time to resolution of acute GvHD after administration of rimiducid
- (iv) Immune reconstitution as determined by T cell subsets up through 180 days
 - a. Absolute CD3 count
 - b. Absolute CD4 count

- c. Absolute CD8 count
- (v) Time-to-immune reconstitution defined by CD3 count > 500 cells/uL; CD4 count > 200 cells/uL; CD8 count of 200 cells/uL
- (vi) Disease-Free/chronic GvHD Survival (DFGS) defined as the first of either disease recurrence, death from any cause, or chronic GVHD
- (vii) Disease status within the following disease indications at 180 days:
 - a. Primary immune disorders as determined by CD3 T cell count ≥ 500 cells/uL and normal levels of IgA and IgM
 - b. Haemoglobinopathies as determined by incidence of RBC transfusion independence for 8 consecutive weeks and untransfused haemoglobin of ≥ 8.5 g/dL

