The resolution of acute GvHD (aGvHD) or chronic GvHD (cGvHD) after administration of rimiducid will be based on the response grading of the GvHD criteria provided in the protocol. The event for this endpoint is any patient who achieved a best overall response (BOR, i.e., either a Complete Response (CR) or Partial Response (PR)) based on aGvHD grading. Only patients experiencing aGVHD who received rimiducid (AP1903) infusion for treatment will be considered for this endpoint. Best overall resolution of aGVHD is defined from the date of AP1903 infusion. The percentage of patients with acute or chronic GvHD, the number of doses of rimiducid, and the best overall response to rimiducid within 7 and 30 days will be presented in listings and summarized. Concomitant medication usage in subjects with acute or chronic GvHD and, further, among those subjects who went on to receive rimiducid, will also be summarized.

Additional analysis and summary statistics will be conducted for resolution of chronic GvHD after administration of rimiducid as well as any case of GvHD (acute or chronic).

(iv) Immune reconstitution as determined by T cell subset counts at day 180

- a. Median and range of CD3 counts at 30, 60, 100 and 180 days
- b. Median and range of CD4 counts at 30, 60, 100 and 180 days
- c. Median and range of CD8 counts at 30, 60, 100 and 180 days

Quantitative assessment of each immune T-cell counts will be performed at various visit time points after transplant as captured in clinical database up to day 180 of follow-up. Analysis and statistical summaries will be performed separately for each T cell subtype assessed. The pattern of each immune reconstitution lab counts will be summarized using graphical summaries and descriptive statistic summary tables including mean (standard deviation), median, and range (minimum, maximum) across the time points assessed. Plots of mean and median cell counts representing measurements over time will be generated to visualize general patterns over time of immune reconstitution.

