7.1.1. Planned Data Outputs

The following outputs are intended to be produced for the study (NB: Numbering is indicative only and may be updated based on CSR requirements):

Tables:

- 14.1.1.1 Number of Subjects by Analysis Population and Disposition
- 14.1.1.2 Summary of Study Analysis Populations
- 14.1.1.3 Major Protocol Deviations and Violations
- 14.1.2.1 Subject Demographics at Baseline
- 14.1.2.2 Baseline Primary Disease Type, Conditioning and Treatment History
- 14.1.2.3 Donor Demographics, Relationships and HLA Typing
- 14.1.4.1 Prior Medications Use
- 14.1.4.2 Concomitant Medications Use
- 14.1.5 Study Treatment Exposure
- 14.2.1.1 Kaplan-Meier Parameter Estimates of Event-Free Survival
- 14.2.1.2 Kaplan-Meier Parameter Estimates of Event-Free Survival: Sensitivity Analysis for Any Grade 2-4 Acute GvHD
- 14.2.1.3 Kaplan-Meier Parameter Estimates of Event-Free Survival: Sensitivity Analysis on Dosing Window
- 14.2.1.4 Kaplan-Meier Parameter Estimates of Event-Free Survival: Sensitivity Analysis for Death from Any Cause
- 14.2.1.5 Kaplan-Meier Parameter Estimates of Event-Free Survival: Sensitivity Analysis for Dose in Subjects with Malignant Disease
- 14.2.2 Cumulative Incidence Function Parameters Time to Transplant-Related or Non-Relapse Mortality
- 14.2.3.1 Cumulative Incidence Function Parameters Time to Acute GvHD Grades 2-4

- 14.2.3.1.1 Cumulative Incidence Function Parameters Time to Acute GvHD: Grade 2 Organ, Grades 3-4
- 14.2.3.2 Cumulative Incidence Function Parameters Time to Acute GvHD Grades 3-4
- 14.2.3.3 Cumulative Incidence Function Parameters Time to Severe Chronic GvHD
- 14.2.3.3.1 Cumulative Incidence Function Parameters Time to Moderate or Severe Chronic GvHD
- 14.2.3.4 Cumulative Incidence Function Parameters Time to Chronic GvHD Mild-Severe

- 14.2.4.1 Kaplan-Meier Parameter Estimates of Time to Resolution of Acute GvHD After Rimiducid Administration
- 14.2.4.2 Kaplan-Meier Parameter Estimates of Time to Resolution of Chronic GvHD After Rimiducid Administration
- 14.2.4.3 Kaplan-Meier Parameter Estimates of Time to Resolution of GvHD (Acute or Chronic) After Rimiducid Administration
- 14.2.4.4 Best Overall Clinical Response to Rimiducid in Subjects with Acute or Chronic GvHD
- 14.2.4.5 GvHD Types and Grades
- 14.2.5 Immune Reconstitution
- 14.2.6 Cumulative Incidence Function Parameters of Time to Immune Reconstitution of CD3, CD4, and CD8 T-cell Counts

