- 16.2.2 Protocol Deviations and Violations
- 16.2.3.1 Analysis Populations
- 16.2.3.2 Subjects Excluded from Efficacy Analysis Populations and Reasons for Exclusion
- 16.2.3.3 Subjects Enrolled into the Study Without Transplantation
- 16.2.3.4 Subjects Receiving Transplantation But No Infusion of BPX-501
- 16.2.4.1 Subject Demographics
- 16.2.4.2 Donor Demographics
- 16.2.4.3 Medical History
- 16.2.4.4 Primary Disease Diagnosis and Treatment History
- 16.2.4.5 Subject/Donor Relation and HLA Typing
- 16.2.4.6 Subject Infectious Disease Testing
- 16.2.4.7 Donor T-cell Leukapheresis and Stem Cell Apheresis
- 16.2.4.8 Medications/Procedures/Treatments Within 30 Days Prior to Conditioning

- 16.2.4.9.1 Concomitant Medications Use
- 16.2.4.9.2 Concomitant Medications Administered for the Treatment of Graft-versus-Host Disease
- 16.2.4.9.3 Concomitant Medications Administered for the Treatment of Graft-versus-Host Disease in Subjects Subsequently Treated with Rimiducid
- 16.2.4.10 Blood Product Transfusion
- 16.2.5.1 HSCT Infusion
- 16.2.5.2 BPX-501 Infusion
- 16.2.5.3 Rimiducid (AP1903) Administration
- 16.2.6.1.1 Listing of Event-Free Survival
- 16.2.6.1.2 Listing of Follow-On Event-Free Survival Events Among Patients with Prior EFS-Qualifying Events
- 16.2.6.1.3 Listing of Overall Survival, Disease-Free Survival, Relapse-Free Survival
- 16.2.6.1.4 Listing of Transplant-Related Mortality or Non-Relapse Mortality
- 16.2.6.2.1 GvHD Types, Severity Score and Time of Occurrence
- 16.2.6.2.2 Listing of Disease-Free/Chronic-GvHD-Free Survival
- 16.2.6.3 Patients Experienced GvHD and Treatment Outcome with Rimiducid (AP1903)
- 16.2.6.4 Mortality and Time of Occurrence
- 12.2.6.5.1 Immune Reconstitution as Determined by Different T-cell Types Counts by Visit Time
- 16.2.6.5.2 Listing of CD3+CD19+ T cells Before and After Treatment with Rimiducid in Subjects with Graft-versus-Host Disease
- 16.2.6.6 Specific Disease Indications Status
- 16.2.6.7 Neutrophil Engraftment and Platelet Engraftment as Determined by Neutrophil Counts and Platelet Counts
- 16.2.6.8 Graft Failures
- 16.2.6.9 Types and Severity of Infectious Complications by Time
- 16.2.6.10 Engraftment
- 16.2.6.11 Hospitalizations
- 16.2.6.12 Listing of Hospitalizations Following AP1903 (Rimiducid) Administration
- 16.2.7.1 All Recorded Adverse Events
- 16.2.7.2.1 Serious Adverse Events
- 16.2.7.2.2 Serious Adverse Events in Subjects Not Infused with BPX-501

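### Time to 'resolution' of acute GvHD after rimiducid counts partial response as resolved, no time-to-complete-response analysis is planned, and the event for chronic and any GvHD is not stated

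*SAP*

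**What the plan says.** SAP 3.2 lists secondary endpoint (iii) as "Time to resolution of acute GvHD after administration of rimiducid" and names no response category. The heading of SAP 6.4.2(iii) extends the label to chronic GvHD and adds in brackets that response to rimiducid is included. The text bases resolution on the protocol's response grading and defines the event as "any patient who achieved a best overall response (BOR, i.e., either a Complete Response (CR) or Partial Response (PR", judged on the acute grading. It then limits the scope: "Only patients experiencing aGVHD who received rimiducid (AP1903) infusion for treatment will be considered for this endpoint". Time runs from the rimiducid infusion.

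For the other two settings the text says only: "Additional analysis and summary statistics will be conducted for resolution of chronic GvHD after administration of rimiducid", and likewise for GvHD of either type. No event is named.

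In SAP 7.1.1, Table 14.2.4.1 is "Kaplan-Meier Parameter Estimates of Time to Resolution of Acute GvHD After Rimiducid Administration", with a matching figure. Tables and Figures 14.2.4.2 and 14.2.4.3 repeat this for chronic GvHD and for either type. Best response appears separately in Table 14.2.4.4, "Best Overall Clinical Response to Rimiducid in Subjects with Acute or Chronic GvHD", and in Listing 16.2.6.3, "Patients Experienced GvHD and Treatment Outcome with Rimiducid (AP1903". SAP 6.4.2(iii) asks for best response within 7 and 30 days.

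**The concern.** A reader of a Kaplan-Meier curve titled time to resolution will take it that the disease has gone. Under the stated event the curve also steps for patients who have improved but still have GvHD. Evaluating rimiducid for GvHD is the SAP's secondary objective (SAP 3.1), and these outputs are its only time-to-event measure of how well the safety switch works. The title therefore claims more than the event supports, always in the favourable direction.

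For chronic and any GvHD the difficulty is different. Two programmers could follow the SAP faithfully, one using CR and the other CR or PR, and produce different tables under the same title. The pooled table could even combine a CR-or-PR event for acute disease with a CR event for chronic disease.

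A secondary point concerns the estimator. The output titles specify Kaplan-Meier, and 6.4.2(iii) gives no rule for a patient who dies before responding.

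**Working it through.** The plan gives no figure for this endpoint, so there is none to reproduce. The check is a comparison of texts, followed by arithmetic on assumed inputs.

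**1. Acute GvHD: label against event.** The endpoint list, the section heading and Table/Figure 14.2.4.1 all say resolution. The event is CR or PR. Of the time-to-event outputs on response to rimiducid (14.2.4.1 to 14.2.4.3), none is defined as time to CR. The BP-004 acute response criteria are not among the documents, so this is a mismatch within the SAP, and no conflict with that protocol is claimed.

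**2. Chronic GvHD: what would follow from CR or PR.** The BP-404 protocol keeps the two ideas apart.
- Section 7.5.1 reserves CR for clearance of every manifestation at every site. PR needs improvement at one site without progression elsewhere.
- Appendix B treats a partial response as improvement short of complete resolution.
- Appendix A.2 gives the skin criterion for PR as "Decrease in NIH Skin Score by 1 or more points".

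Take a patient whose only involved organ is skin and whose score falls from 3 to 2. By Appendix A.2 this is a PR. Under a CR-or-PR event the patient would be resolved. Under the global scoring in Appendix A.1, one organ at score 2 is still moderate chronic GvHD, a grade that SAP 6.4.1 includes in severe GvHD for EFS. SAP section 2 lets the SAP override the protocols, so this is an ambiguity to settle, not a standing contradiction.

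**3. Size of the overstatement.**

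Proportion resolved as written = (CR + PR-only)/N. Proportion by CR = CR/N. Difference = PR-only/N.

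N is not given. Per PR-only patient, for assumed N:

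| N | Added to the resolved proportion |
|---|---|
| 10 | 1/10 = 10 points |
| 20 | 1/20 = 5 points |
| 40 | 1/40 = 2.5 points |

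Equivalently, the difference is the overall response rate times the PR-only share of responders. With an assumed response rate of 60% and shares of 10%, 25% and 50%, the CR proportion is 54%, 45% and 30%. With 80% it is 72%, 60% and 40%. The gap therefore runs from 6 to 40 points across these assumptions.

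The only response data in the documents are in Protocol 4.1.3: three patients in an earlier phase I study, all with complete resolution of acute GvHD. That is 0 of 3 PR-only. The exact upper 95% limit is 1 − 0.025^(1/3) = 0.708, so the interval is 0% to 70.8% and settles nothing.

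**4. Timing.** Best overall response is a category, not a date, and the SAP does not say which assessment dates the event. If the first response is used, a patient who passes through PR to CR is counted earlier than by CR. The curve can then shift even when the final proportion does not.

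**5. Death before response (secondary point).** The SAP treats death as a competing event for GvHD onset (6.4.2(ii)), immune reconstitution (6.4.2(v)) and engraftment (6.4.3(ii) and (iii)), but not here. Assume N = 20, 16 events, 2 deaths censored, and 2 non-responders censored at the end:

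| Deaths occur | 1 − KM |
|---|---|
| before any event | 1 − 2/18 = 88.9% |
| after 8 events | 1 − (12/20)(2/10) = 88.0% |
| after 15 events | 1 − (5/20)(2/3) = 83.3% |
| after all 16 events | 1 − 4/20 = 80.0% |

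Cumulative incidence with death competing is 16/20 = 80% in every row.

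**The case against.** The strongest reply is that the SAP uses resolution as a defined term. The heading says response is included, the event is stated openly, and Appendix B of the protocol adds the word complete when it means CR. Best response at 7 and 30 days is tabulated and listed, so the CR count may be visible there. SAP 7.1 allows output titles to change without a revision, and 6.7 leaves room for further exploratory analyses. The governing BP-004 protocol is not available to check. The numerical inputs are assumed, and some of them give no effect. The estimator point rests on output titles, while SAP 6.2.1 allows Kaplan-Meier or Nelson-Aalen as suits the endpoint.

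Much of this stands. The disclosure and the best-response table limit misreading, the size cannot be known from the documents, and the skin example applies only if CR or PR is used for chronic disease. It is also consistent for a patient to have an EFS event and later a partial response. The example shows only how much disease can remain in a patient labelled resolved.

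The rest does not remove the point. No CR/PR split is promised for Table 14.2.4.4, and a category at two landmarks is not a time-to-CR estimate. Freedom to retitle or explore does not commit anyone to doing so. Carrying the acute event over to chronic disease would be inference, because the text restricts it to acute patients. The general wording in 6.2.1 does not override output titles that name Kaplan-Meier.

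**Conclusion.** The concern holds. For acute GvHD, the SAP as written counts PR-only patients as resolved and plans no time-to-CR analysis. For chronic and any GvHD it does not say which response is the event.

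The direction is certain: at any time the CR-or-PR curve lies at or above the CR curve. The magnitude is not known. It depends on how many treated patients are PR-only, which the documents do not give, and the excess in the final proportion is zero if there are none. The Kaplan-Meier point is secondary. On the assumed inputs it adds between 0 and 8.9 percentage points, depending on when the deaths fall.

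The consequence is confined to a descriptive secondary endpoint, and the primary EFS analysis is untouched. It should be corrected before the outputs are produced, but it does not threaten the trial's main conclusion.

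**What to change.** Amend SAP 6.4.2(iii) as follows.

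- Keep the CR-or-PR analysis, but call it time to first response (CR or PR).
- Add time to resolution, defined as first CR under the protocol grading the SAP already cites.
- State both events for acute, chronic and any GvHD.
- Date each event at the first qualifying assessment after rimiducid.
- Estimate both by cumulative incidence with death as a competing event, matching the SAP's treatment of GvHD onset, immune reconstitution and engraftment.
- Retitle Tables and Figures 14.2.4.1 to 14.2.4.3 to match.

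The cost is some SAP wording and one additional set of outputs. CR and PR grades are already needed for Table 14.2.4.4, so no new data are required, and no dosing or clinical rule changes. The price is a possibly less favourable resolution rate and fewer events in what may be a small subset.
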